## 4.6 Study Patients

### 4.6.1 Disposition of Patients

A clear accounting of the disposition of all patients who enter the study will be provided, from screening to study completion. Summaries will include:

- number of patients screened,
- number of patients randomized,
- number of patients dosed,
- number of patients in each analysis sets,
- number of patients who completed study (Day 60 assessment),
- number of patients who withdrew early from the study (including reasons for early withdrawal).

By-patient listings of eligibility details, randomization details, visit dates and withdrawal/study completion details (including reason for discontinuation and duration of treatment prior to discontinuation) will be provided. Disposition data will be listed and summarized for All Screened, and also summarized for mITT set.

### 4.6.2 Protocol Deviations

All identified protocol deviations throughout the study will be listed prior to database lock. Protocol deviations will be identified and classified into major or minor. Major protocol deviations are defined as those that could have a significant effect on the subject's safety, rights, or welfare and/or on the integrity of the study data.

During the blinded data review meeting (BDRM), the subject's assignment to or exclusion from any analysis set will be discussed in detail. The decisions made during the BDRM will be documented in the BDRM minutes and agreed upon prior to database lock and unblinding for final analysis.

The following summaries will be provided for mITT set:

- all major protocol deviations related to inclusion and exclusion criteria,
- all other major protocol deviations.

A by-subject listings will be provided for all reported protocol deviations.

#### 4.7 Demographic and Other Baseline Characteristics

Demographic and other baseline characteristics will be summarized by treatment group, for both treatment groups combined (Total) and All Patients using the mITT set. The summaries provided will include the following:

- Demographic variables:
  - Age (continuous and categorical [ $<65$  years;  $\geq 65$  years]),
  - Sex,
  - Race,
  - Ethnicity,
  - Baseline height,
  - Baseline weight,
  - Baseline Body Mass Index (BMI) continuous and categorized ( $<30$ ,  $\geq 30$ ) and ( $<35$ ,  $\geq 35$ ).

Age will be calculated based on date of randomization. BMI will be calculated based on baseline height and weight as weight (kg) / height (m^2).

- Baseline disease characteristics:
  - Baseline WHO Ordinal Scale,
  - Baseline maximum temperature measurements,
  - Baseline oxygen utilization (yes, no), if yes method of Oxygen delivery,
  - Baseline oxygen saturation  $\leq 86\%$ ,
  - Days since onset of COVID-19 related symptoms,
  - Days hospitalized prior Day 1.

Technical Note: Onset of COVID-19 related symptoms are documented on the Medical History Form. Use the earliest MH record related to COVID-19 and derive as: date of study drug administration – date of start of first MH record related to COVID-19.

- Risk Factors at Baseline:
  - subjects with Age  $\geq 65$  years,
  - subjects with Obesity (BMI  $\geq 30$ ),

---

- subjects with Morbid Obesity (BMI  $\geq 35$ ),
- subjects with Diabetes (MH PT: type 2 diabetes mellitus, diabetes mellitus),
- subjects with Hypertension (MH PT: hypertension),
- subjects with Coronary Artery Disease (MH PT: coronary artery disease),
- subjects with Chronic Kidney Disease (MH PT: chronic kidney disease),
- subjects with Chronic Respiratory Disease (MH PT: Asthma; Chronic obstructive pulmonary disease; Sleep apnoea syndrome),
- subjects with Cardiovascular Disease (MH SOC: Cardiac Disorders),
- subjects with 1, 2, 3, 4, 5, 6, or 7 risk factors present at baseline.

**Technical Note:** Medical History Terms that are related to COVID-19 will not be considered for risk factors. The risk BMI  $\geq 30$  and/or  $\geq 35$  will be counted as only one risk factor per subject and further, risk of coronary artery disease and/or cardiovascular disease will only be counted as one risk factor per subject.

- Medical history will be reported by system organ class (SOC) and preferred term (PT) as coded using the Medical Dictionary for Regulatory Activities (MedDRA) Version 23.0 or higher. Two summaries will be provided 1) non-COVID-19 related and 2) COVID-19 related.

By-patient listings of demographic data, other baseline characteristics (as summarized above) and medical history will be provided. Reproductive system findings including child-bearing potential and pregnancy test results will be listed only.

#### 4.8 Concomitant Medications and Procedures

Medications will be coded using Anatomical Therapeutic Chemical (ATC) Classification codes by WHO Drug Global version Mar 2019 Format C3. Prior and concomitant medications will be summarized by ATC class level II, and Preferred Term, using the Safety Set.

Medication start and stop dates will be compared to study drug administration date to allow medications to be classified as either prior only, both prior and concomitant, or concomitant only. Missing or partial start dates will be imputed as described in [Section 4.3](#).

Medications that start and stop prior to study drug administration will be classified as prior only. If a medication starts before study drug administration and stops on or after study drug administration or stop date is missing, then the medication will be classified as both prior and concomitant. Medications will be classified as concomitant only if they have a start date on or after study drug administration.

In the summary of prior and concomitant medications, each subject will be counted once within each unique term. For example, if a subject takes amoxycillin on 2 separate occasions, the subject is counted only once under the corresponding ATC class.

Summaries and by-subject listings will be given for Safety Set. The summary will group the medication by Prior only, Prior and Concomitant and Concomitant only.

Listings will include medication/therapy start and end date:time or ongoing status, dose, route, frequency, primary indication for the medication, AE term if applicable, medical history term if applicable and concomitant medication flag (Prior only, Prior and Concomitant, Concomitant only).

Additionally, number of patients taking Remdesivir (ATC Level 2 code “J05”) and/or Dexamethasone or other glucocorticosteroids (ATC Level 2 code “H02”) and/or Convalescent Plasma (ATC Level 2 code ‘J06) flagged as “Prior and Concomitant” or “Concomitant only” will be provided by treatment group for the Safety Analysis Set.

## 4.9 Efficacy Evaluation

### 4.9.1 Differences from Interim Analysis

No changes from Interim Analysis.

### 4.9.2 Multiple Comparisons and Multiplicity

Given the exploratory nature of this study, all comparisons of treatment groups versus placebo will be interpreted in an exploratory manner and thus no adjustments for multiplicity will be performed. P-values provided are deemed to be exploratory.

### 4.9.3 Primary Efficacy Analyses

See [Section 4.10.2](#).

### 4.9.4 Key Secondary and Exploratory Efficacy Analyses

Secondary and exploratory endpoints will be analyzed according to the type of endpoint as described below. If data are sparse for any of the exploratory endpoints, summaries may be limited to descriptive statistics of available data or listings only as appropriate.

Time to event endpoints will be analyzed using Kaplan Meier method. The total number of patients with an event, the total number censored and Kaplan-Meier survival estimates with associated 95% CI (25% percentile, median, and 75% percentile) will be presented by treatment group. Further, crude proportions for having the event at timepoints with events observed (derived as: cumulative number of subjects with events / number of subjects in treatment group at baseline) along with 95% Wilson Score intervals with continuity correction will be provided.

Further, Kaplan-Meier estimates at 5, 6, 7, 10, 14 and 28 days from first study drug administration will be provided with associated 95% CI.

A survival plot will be produced with the probability of an event (0% to 100%) along the Y-axis and time in days along the X-axis.

The hazard ratio of ATYR1923 1 mg/kg versus Placebo, ATYR1923 3 mg/kg versus Placebo, and ATYR1923 Total versus Placebo with corresponding 95% CI and p-values will be estimated from a single Cox Proportional Hazards model.

All efficacy summaries and analyses will be based on mITT Set, unless otherwise stated.

#### 4.9.4.1 Secondary Efficacy Analyses

##### Time to hospital discharge

Time to hospital discharge will be calculated as:

discharge date – study drug administration date.

Patients who die in hospital will be censored at death date. Patients still in hospital at EOS will be censored at EOS visit.

For imputation of partial missing dates for death or discharge from hospitalization see [Section 4.3.2](#).

Additionally, time to hospital discharge will be analyzed using an adapted derivation: discharge date – randomization date. The same rules for handling of hospitalized or discontinued patients and partial missing data applies as mentioned above. Related output will be noted as sensitivity analysis.

Time to hospital discharge will be analyzed based on mITT and EE Set. Sensitivity analysis for time to hospital discharge will be analyzed based on mITT only.

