### 4.2 General Presentation Considerations

**Baseline:** the last available pre-treatment assessment, unless otherwise specify. All assessments should have time collected. If time is not collected and date of assessment is the same as study drug administration date then assessment will be assumed to be collected prior to treatment unless schedule of assessments and protocol indicate planned collection is always after dosing.

For baseline of oxygen use, total oxygen use in 24 hours before drug administration date.

**Day-of-Discharge (DoD):** day when patient is discharged from the hospital.

**Date of discharge:** date patient is discharged from the hospital.

**Early Termination (ET):** day when patient withdraws from the study before completion.

**End-of-Study (EOS):** the EOS assessment is at Day 60 for patients who complete the study.

**End of study date:** date of EOS assessment (Day 60) if patient completes the study or date of early withdrawal if patient discontinues early, or date of death.

**Study Day:** <Assessment Date> - study drug administration date + 1 if <Assessment Date> is on or after study drug administration date. <Assessment Date> - study drug administration date, if <Assessment Date> is before study drug administration date.

Durations are generally calculated as the stop date - start date +1, if not otherwise stated.

For elapsed time (eg, time since the initial diagnosis) is calculated as reference date - event date.

If more than one laboratory value is available for a given study day, the last valid observation will be used in summaries, unless otherwise stated. If it is not possible to determine which is the last measurement due to missing times, then the average of all measurements for that study day will be used as the value for that study day. All observations will be presented in listings.

Laboratory data will be presented in standard units.

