##### Time to recovery

Time to recovery is calculated as:

date of first time WHO scale score  $\leq 3$  - study drug administration date; or date of discharge from hospital - study drug administration date, whichever occurs first.

In the case that a patient does not reach WHO scale score  $\leq 3$  criteria, the patient will be censored at EOS visit.

Additionally, time to recovery will be analyzed using an adapted derivation:

date of first time WHO scale score  $\leq 3$  – randomization date or date of discharge from hospital  $\leq 3$  – randomization date, whichever occurs first. Related output will be noted as sensitivity analysis.

Time to recovery will be analyzed based on mITT and EE Set. Sensitivity analysis for time to recovery will be analyzed based on mITT only.

Time to recovery with WHO scale score  $\leq 3$  without supplemental oxygen

Some patients were discharged from hospital while still using supplemental oxygen and so an additional sensitivity analysis will be performed to evaluate the impact for time to recovery. The following Pseudo-Code will be applied in the given order to derive time to recovery without supplemental oxygen:

1. Derive time to event 'T' as date of first time WHO scale score  $\leq 3$  - study drug administration date; or date of discharge from hospital - study drug administration date, whichever occurs first.
2. For subjects who discharged earlier than reporting an WHO scale score  $\leq 3$  apply the following checks:
  - a. If an supplemental oxygen dose of '0' is reported at day of discharge keep T.
  - b. If an supplemental oxygen dose of '0' is already reported one day prior day of discharge use T-1.
  - c. If an supplemental oxygen dose of  $>0$  is reported at day of discharge and discharge reason indicate that the subject is not on oxygen (e.g. "On Room Air" or "Weaned off O2") keep T.
  - d. If an WHO scale score  $\geq 4$  is reported at day of discharge and an WHO scale score  $\leq 3$  is reported one day after discharge use T+1.
  - e. If an WHO scale score  $\geq 4$  is reported at day of discharge and an WHO scale score  $\leq 3$  is reported two days after discharge use T+2.
  - f. If an WHO scale score  $\geq 4$  is reported at day of discharge and none of the criteria above are met use T+2.
3. In the case that a patient does not reach WHO scale score  $\leq 3$  criteria or has no discharge event, the patient will be censored at EOS visit.

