Days with fever up to Day 14 will be used as a sensitivity analysis. Days will be calculated the same as described for Days of supplemental oxygen (O2) up to Day 14.

Change from baseline in WHO Ordinal Scale score

The description of the WHO Ordinal Scale score is shown in [Section 6.2](#). The Number and percentage of patients on WHO Scale scores and change from baseline (-7, -6, -5, -4, -3, -1, 0, 1, 2, 3, 4) will be presented by visit. Shift table will be presented by visit as well.

Simple Ordinal logistic regression on the WHO Scale score at each visit (Days 5, 7, 14, 28, and 60) will be performed to compare ATYR1923 1 mg/kg versus Placebo and ATYR1923 3 mg/kg versus Placebo. Firth logistic regression ([Firth, 1993](#)) on the collapsed WHO Ordinal Scale (0-3 versus 4-8) at each visit (Days 5, 7, 14, 28, and 60) will be performed as well.

Distribution of WHO Ordinal Scale at 1, 2, 3, 4, 5, 6, 7, 10, 14, 28 and 60 days will be visualized by treatment group using an stacked bar chart. These figures will only consider scheduled assessments and in case the scheduled assessment is not available the mapped unscheduled TC follow up assessments as defined in [Section 4.2](#).

Time to Improvement in Clinical Status

Time to improvement in days is the time in which the patient sees a decrease after study treatment in the WHO Ordinal Scale score from baseline by at least 1 point, derived as:

date of decrease in WHO scale compared to baseline by at least 1 point - study drug administration date; or date of discharge from hospital - study drug administration date, whichever occurs first.

In the case that a patient has not decreased in the WHO scale or withdraws from the study, they will be censored at EOS date. Time to improvement will be analyzed using the Kaplan-Meier methods and Cox Proportional Hazards model as described in the above.

Repeat analysis above for improvement of WHO Ordinal Scale score by at least 2 points.

Additionally, time to improvement will be analyzed using an adapted derivation: date of decrease in WHO scale compared to baseline by at least 1 point - randomization date; or date of discharge from hospital - randomization date, whichever occurs first.

Related output will be noted as sensitivity analysis.

Time to improvement (by at least 1 and 2 points) will be analyzed based on mITT and EE Set. Sensitivity analysis for time to improvement will be analyzed based on mITT only.

*All-cause mortality*

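### Kaplan-Meier output for discharge and improvement censors deaths, so it overstates the chance of the event when a patient dies first; the recovery rule for deaths and withdrawals is ambiguous

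*SAP*

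**What the plan says.** **Discharge** (SAP 4.9.4.1, Time to hospital discharge): "Patients who die in hospital will be censored at death date".

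**Improvement** (SAP 4.9.4.1, Time to Improvement in Clinical Status): for patients without the event, or who withdraw, "they will be censored at EOS date". SAP 4.2 gives the end of study date as Day 60 for completers, otherwise "date of early withdrawal if patient discontinues early, or date of death". Deaths before improvement are therefore also censored at death, although this section does not mention death.

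**Recovery** (SAP 4.9.4.1, Time to recovery): without the event, "the patient will be censored at EOS visit". The version without supplemental oxygen uses the same rule. Neither names deaths or withdrawals. SAP 4.2 says of this visit that "the EOS assessment is at Day 60 for patients who complete the study".

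**Output** (SAP 4.9.4): "Time to event endpoints will be analyzed using Kaplan Meier method", giving quartiles and estimates at Days 5, 6, 7, 10, 14 and 28. Also, "A survival plot will be produced with the probability of an event (0% to 100%) along the Y-axis". Hazard ratios come from a single Cox model. Competing risks and cause-specific hazards are not mentioned. The same section plans crude proportions, defined as "cumulative number of subjects with events / number of subjects in treatment group at baseline", with Wilson intervals.

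**Oxygen days** (SAP 4.9.4.1): oxygen already running at dosing is counted from dosing. For patients who die or withdraw on oxygen, the formula counts from the oxygen start date.

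**The concern.** Censoring assumes that the patient could still have the event later. That suits a patient lost to follow-up, but not one who died in hospital. With deaths censored, one minus Kaplan-Meier is not the probability of having been discharged. It shares the dead patient's chance of discharge among those still at risk.

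The SAP presents this curve as the probability of the event. In an arm with an early death the report would show a Kaplan-Meier percentage and a lower crude proportion for the same patients, with nothing to explain the gap. With about 10 patients per arm, one death is enough to show it. If all-cause deaths total three or fewer, mortality appears only as a listing, so a reader has less to set against the curve.

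If recovery is read as holding deaths to Day 60, it follows a different rule from discharge and improvement, and the curves are not comparable.

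**Working it through.** The documents give no death rate, event rate or power calculation, so there is no planned time-to-event figure to reproduce. From the SAP come the arm size (30 patients, 1:1:1, so about 10 per arm), the 60-day follow-up and the estimation days. Event and death times below are assumed.

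**Step 1. Early deaths, no other loss.** Arm of 10 with *k* deaths on Day 4. Discharges fall on Days 5, 6, 7, 8, 9, 10 and 12, plus Day 15 if *k* is 2 or less, plus Day 20 if *k* = 1. After *j* discharges:

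- Kaplan-Meier with deaths censored: *j*/(10 − *k*)
- cumulative incidence with death competing (Aalen-Johansen): *j*/10, equal to the planned crude proportion.

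| Deaths | Day 7 (*j* = 3) | Day 10 (*j* = 6) | Day 28 (*j* = 10 − *k*) |
|---|---|---|---|
| 1 | 3/9 = 33% v 30% | 6/9 = 67% v 60% | 9/9 = 100% v 90% |
| 2 | 3/8 = 38% v 30% | 6/8 = 75% v 60% | 8/8 = 100% v 80% |
| 3 | 3/7 = 43% v 30% | 6/7 = 86% v 60% | 7/7 = 100% v 70% |

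Quartiles, taken as the first day the curve reaches the level (Kaplan-Meier v true):

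| Deaths | 25th | Median | 75th |
|---|---|---|---|
| 1 | 7 v 7 | 9 v 9 | 12 v 15 |
| 2 | 6 v 7 | 8 v 9 | 10 v 15 |
| 3 | 6 v 7 | 8 v 9 | 10 v never reached |

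If software takes the midpoint when a curve sits exactly on the level, the medians become 9 v 9.5, 8.5 v 9.5 and 8 v 9.5, and the two-death 75th percentile becomes 11 v 15.

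**Step 2. Death after the last event.** Discharges on Days 5 to 10, 12, 13 and 14, with a death on Day 30: 30%, 60% and 90% at Days 7, 10 and 28 by both methods.

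**Step 3. Deaths and a withdrawal.** Three deaths on Day 4, with the Day 6 discharge replaced by a withdrawal on Day 6. Five patients are then at risk at Day 7.

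- Kaplan-Meier, Day 7: 1 − (6/7)(4/5) = 31%. Days 10 and 28: 83% and 100%.
- Aalen-Johansen, Day 7: 1/10 + 0.6 × 1/5 = 22%. Days 10 and 28: 58% and 70%.
- Crude: 2/10, 5/10 and 6/10, so 20%, 50% and 60%.

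The crude proportion matches cumulative incidence only while nobody is lost for other reasons.

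**Step 4. Constant hazards.** Total hazard 0.1 per day, with a share *m* of exits being deaths. At Day 28 Kaplan-Meier gives 1 − exp(−2.8(1 − *m*)); the truth is (1 − *m*)(1 − exp(−2.8)). For *m* = 5, 10, 20 and 30%: 93.0, 92.0, 89.4 and 85.9% against 89.2, 84.5, 75.1 and 65.7%.

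**Step 5. Hazard ratio.** Comparator arm discharged on Days 4, 5, 6, 7, 8, 9, 10, 12, 15 and 20. In the other arm the slowest to recover die. Cox model, Efron ties, 95% intervals in brackets:

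| Deaths | Deaths censored (SAP) | Deaths held to Day 60 |
|---|---|---|
| 1 v 0 | 1.28 (0.50–3.26) | 0.90 (0.37–2.21) |
| 2 v 0 | 1.52 (0.56–4.14) | 0.77 (0.30–1.96) |
| 3 v 0 | 1.72 (0.58–5.12) | 0.64 (0.24–1.70) |

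The columns answer different questions: the discharge rate among patients still alive in hospital, and discharge with death counted as never discharged. In simulations with balanced deaths (1 v 1 to 3 v 3), the median hazard ratios were 0.97–1.04 and 0.99–1.02, so the choice hardly mattered.

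**Step 6. Recovery.** In the one-death arm of Step 1, Day 28 recovery is 100% if the death is censored at death and 90% if held to Day 60. Replace the death by a withdrawal and the same two figures appear with nobody dead. There the 90% comes from treating a withdrawn patient as observed without recovery to Day 60.

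**Step 7. Oxygen days.** For a patient who dies on oxygen on Study Day 10, with oxygen started 1, 3 or 7 days before dosing, the literal formula gives 11, 13 or 17 days. Counting from dosing gives 10.

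**The case against.** **The correct figure is already planned.** This is the strongest point, and it partly stands. The crude proportions equal cumulative incidence when death is the only early exit. Recovery by Day 14 and Day 28 uses the full set as denominator (SAP 4.3.1), and mortality is reported. None of these corrects the quartiles, fixed-day estimates or plot, and Step 3 shows the crude figure falling short once someone withdraws.

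**The effect may be small or absent.** This stands. It needs a death followed by other patients' events, the median barely moves, and every death rate above is assumed.

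**The hazard ratio is invalid and favours the arm with more deaths.** A reader might infer this from Step 5, but the documents do not support it. Model and censoring rule are both stated, and the result is a valid cause-specific ratio. The reversals need unbalanced deaths among the slowest to recover, and the intervals are very wide. Only the label is missing.

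**Recovery has no death rule.** This also goes too far. The end of study date in SAP 4.2 offers one natural reading and Day 60 another. The text is ambiguous, not silent.

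**The oxygen formula is an error.** The sentence may be meant only to supply an end date. The SAP's worked withdrawal example, (3/5) × 14 = 8.4 days, counts from Day 1, which favours the harmless reading although it belongs to the Day 14 sensitivity analysis. One clarifying line is enough.

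**The death rule was chosen after unblinding.** The revision history does not list it among the changes in versions 2.0 or 3.0, so nothing supports that inference.

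**Conclusion.** The point holds for the Kaplan-Meier output of discharge and improvement. With one to three deaths before the event in an assumed arm of 10, the Day 28 probability is overstated by 10 to 30 percentage points. The 75th percentile comes several days early, or appears when it is never truly reached. The median shifts by at most one day (a day and a half under the midpoint convention). With no such death, or only deaths after the arm's last event, nothing changes.

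For recovery, the wording leaves open whether deaths and withdrawals are censored when they occur or at Day 60, and the choice can change the curves. The hazard-ratio label and the oxygen start date are clarifications.

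The study is unpowered, its primary endpoint is safety and SAP 4.9.2 treats all comparisons as exploratory. It should be fixed because the printed figures would mislead, not because a formal decision would go wrong.

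**What to change.** 1. For discharge, both versions of recovery, and improvement, take the quartiles, fixed-day estimates and plots from the Aalen-Johansen cumulative incidence with death as a competing event. Label these as post-unblinding, in line with the revision history, and as post hoc under SAP 3.2. The planned Kaplan-Meier output may stay beside them if it is not described as the probability of the event.
2. Keep the planned Cox model and label its hazard ratio cause-specific. Add a sensitivity analysis with deaths kept event-free to Day 60.
3. Under Time to recovery, replace the reference to the EOS visit with explicit rules matching the other endpoints: withdrawals censored at the withdrawal date, deaths treated as a competing event.
4. As a minor clarification, state that oxygen days for patients who die or withdraw on oxygen start at the later of oxygen start and dosing.

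The cost is SAP wording and light programming, with no new data. One more post-unblinding change goes on record. Estimates in arms with early deaths become less favourable. Recovery results may also change because of withdrawals, even with no deaths, if the EOS visit was being read as Day 60.
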